5 GENERAL ANALYSIS CONSIDERATIONS

Due to the small number of enrolled subjects, efficacy and safety variables will be provided in data listings; no tabular summaries will be generated.

5.1 Analysis Populations

The following population is used:

Intention-to-treat (ITT) Population: all subjects who have received BMN 270 infusion.

Data listings will be provided for ITT population.

5.2 Treatment Group Presentation

Only listings will be provided due to the small number of enrolled subjects.

5.3 Study Day Derivation

Study day is assigned as follows:

- The investigational product infusion date is designated as Day 1.
- For visit days after infusion, study day = visit date Day 1 date + 1.
- For visit days prior to infusion, study day = visit date Day 1 date (thus, study days for screening visits are negative numbers).

5.4 Baseline Value

The baseline values are calculated using data during the one year prior to enrollment for the following endpoints:

- annualized utilization of exogenous FVIII replacement therapy,
- the annualized number of treated bleeding episodes,

The baseline values of other assessments are defined as the last available measurement prior to the administration of investigational product.

5.5 Handling of Dropouts and Missing Data

If a subject withdraws from the study prematurely, the subject will be asked to complete an Early Termination Visit (ETV), the data from which will be included in data listings.

Missing dates or partially missing dates will be imputed conservatively for concomitant medications and adverse events (AEs) to ensure that an AE is considered treatment emergent when possible and the duration is the longest possible duration.

Other missing data will not be imputed unless otherwise stated.

6 SUBJECT DISPOSITION

A data listing will present for each subject the date of informed consent, date of enrollment, date of infusion, end of study date, and whether the Week 26 visit was completed and whether the Week 52 visit was completed. The screening information including the screen failure reasons will also be provided in a listing.

7 DISCONTINUATION AND COMPLETION

For subjects who prematurely discontinue study participation, a data listing will present for each subject the date of exit from the study and the reason for exit from the study.

8 PROTOCOL DEVIATIONS

The trial's Study Specific Guideline for Managing Protocol Deviations defines protocol deviations, including whether they are minor or major. A data listing of protocol deviations will be provided.

9 DEMOGRAPHICS AND BASELINE CHARACTERISTICS

Subject demographic and baseline characteristics to be provided in data listings include:

- age at enrollment (year)
- sex (Female/Male)
- ethnicity
- race
- height (cm)
- weight (kg)
- BMI (kg/m^2)
- baseline disease characteristics including
 - o date of diagnosis of hemophilia A
 - o time since diagnosis of hemophilia A (year)
 - o type of FVIII treatment for hemophilia A (prophylaxis/on-demand)
 - o any history of FVIII inhibitor (Yes/No/Unknown)
 - o date of assessment and results for FVIII genotyping
 - o any target joints/bleeding sites (Yes/No)
 - o motion limitation for target joint/bleeding site (Yes/No)
 - o surgery/synovectomy on target joint/bleeding site (Yes/No)
 - o ambulatory assist device requirement (Yes/No)
- baseline FVIII activity (IU/dL)
- baseline annualized utilization (IU/kg) of exogenous FVIII replacement therapy
- baseline ABR (bleeds/year) for treated bleeds

10 MEDICAL HISTORY

Medical history will be coded using the most current version of Medical Dictionary for Regulatory Activities (MedDRA) at the time of coding. Medical history will be provided in a data listing. The following targeted medical history will be provided in a separate data listing:

- history of exposure to hepatitis B (Yes/No) and current infection status (Yes/No)
- history of exposure to hepatitis C (Yes/No) and current infection status (Yes/No)
- history of liver disease (Yes/No)
 - o if Yes: liver biopsy (Yes/No) and findings; liver imaging (Yes/No), type, and findings
- history of HIV (Yes/No)
 - o if Yes: current CD4 count, current viral load, and whether patient is on HAART

11 PRIOR AND CONCOMITANT MEDICATIONS/PROCEDURES

Prior and concomitant medications are defined as follows:

- prior medication any medication taken prior to the initiation of the investigational product and within 30 days prior to screening.;
- concomitant medication any medication taken after initiation of the investigational product.

All medications will be coded using the current version of the World Health Organization Drug (WHO Drug) Dictionary. Prior and concomitant medications will be provided in a data listing.

Corticosteroid usage including type (i.e., whether for therapeutic or prophylactic purpose), dosage, time to initiation of treatment, and total duration of treatment will be provided in a data listing.

12 EXTENT OF EXPOSURE TO INVESTIGATIONAL PRODUCT

Each subject will receive a single intravenous infusion of BMN 270, and the volume of infusion will depend on subject's weight. A data listing of drug exposure including actual dose (vg/kg), change of dose, rate of dose will be provided.

13 EFFICACY EVALUATIONS

FVIII activity levels over time and bleeding episodes will be provided in data listings based on ITT population; no tabular summaries will be generated.

Listings for annualized bleeding rate (ABR) for treated bleeds, annualized FVIII use and annualized FVIII infusion rate will also be provided.

Annualized bleeding rate (ABR) (counts/yr.)

 $= \frac{\text{Number of bleeding episodes during calculation period}}{\text{Total number of days during the calculation period}} \times 365.25$

Annualized FVIII use (IU/kg/yr.)

 $= \frac{\text{Sum of FVIII use(IU/kg) during calculation period}}{\text{Total number of days during the calculation period}} \times 365.25$

Annualized FVIII infusion rate (count/yr.)

 $= \frac{\text{Number of FVIII replacement infusions during calculation period}}{\text{Total number of days during the calculation period}} \times 365.25$

The calculation period in the above formulas for post-baseline values will be Weeks 1-4, Weeks 5-26, Weeks 5-52, and Weeks 5 and beyond.

Data listings for following patient-reported outcomes (PROs) will be provided to assess subject quality of life (QoL) during the study:

- Haemo-QoL-A
- EQ-5D-5L
- Haemophilia Activities List (HAL)
- Work Productivity and Activity Impairment plus Classroom Impairment Questions: Hemophilia Specific (WPAI+CIQ:HS)

14 SAFETY EVALUATIONS

Safety will be assessed by adverse event reporting; clinical laboratory assessments, with particular attention to liver function; vital signs assessments; physical examinations; and immunogenicity. No formal statistical testing will be performed or tabular summaries generated, only data listings will be provided. The safety analysis will be based on the ITT population.

14.1 Adverse Events

A TEAE is defined as any AE that newly appeared or worsened in severity following initiation of investigational product administration. Adverse events will be coded in accordance with Medical Dictionary for Regulatory Activities (MedDRA). TEAE will be flagged in listings.

An adverse drug reaction (ADR) is any AE for which there is a reasonable possibility that the investigational product caused the AE. The investigator will assess the causality for individual AEs, applying the guidance specified in the protocol, and those assessed as study drug-related will be considered ADRs.

A serious adverse event (SAE) is any untoward medical occurrence that at any dose meets one or more of the seriousness criteria enumerated in the protocol. AE severity, not equivalent to seriousness, will be assessed using the protocol defined categories using the NCI CTCAE v4.03.

All bleeding events and suspected bleeding events, regardless of the need for exogenous FVIII therapy as treatment, should be captured in subject diaries and recorded on the designated bleeding eCRF. Bleeding events and suspected bleeding events should not be reported as adverse events, with the following exception:

All bleeding events and suspected bleeding events which meet one or more of the
criteria for being serious (refer to the Protocol Section 10.2) should be reported as
serious adverse events (whether or not they are bleeding events that are normal
sequelae of hemophilia, and whether or not they required exogenous FVIII as
treatment).

The study AE reporting period is as follows: After informed consent but prior to initiation of study drug, only SAEs associated with any protocol-imposed interventions will be reported. After informed consent is obtained and following infusion of study drug, the reporting period for all non-serious AEs and SAEs begins and continues for approximately 5 years or until study discontinuation/termination, whichever is longer.

If the onset date or end date of an AE is partial, the same imputation rules described in Section 56 will be applied.

14.1.1 All Adverse Events

All AEs will be provided in a data listing, including system organ class (SOC) and preferred term (PT).

14.1.2 Drug-Related Adverse Events

The AE listing will include assessment by the investigator(s) as to whether the AE was related to investigational product (i.e., an ADR).

14.1.3 Deaths and Serious Adverse Events

Serious adverse events will be provided in a data listing, including assessment by the investigator(s) as to whether the SAE was related to investigational product (i.e., a serious ADR). Deaths (i.e., SAEs resulting in death) will be provided in a separate data listing.

14.1.4 Adverse Events Causing Early Discontinuation

AEs resulting in discontinuation of study will be presented in a data listing.

14.1.5 Events of Interest

The following events of interest, which include EOSI defined in the protocol, will be provided in a data listing for each type of EOSI.

Table 1: Sponsor-defined Events of Special Interest

Name of EOSI	Definition
ALT elevations reported as EOSIs	Reported as EOSIs with AE preferred term = "Alanine"
	aminotransferase increased"
AEs of liver dysfunction	MedDRA search strategy
	High level term (HLT) = "Liver function analyses"
Potential Hy's law cases	• ALT or AST \geq 3x ULN and serum TBL $>$ 2x ULN
	Assessments of ALT/AST and TBL must be on the same day
Infusion related reactions	Any AE occurring during BMN 270 infusion or up to 48 hours
	post-infusion ^[a]
Systemic hypersensitivity	MedDRA search strategy
	Hypersensitivity (SMQ) – narrow scope
	Occurring during BMN 270 infusion or up to 48 hours post-
	infusion ^[a]
Anaphylactic or anaphylactoid	MedDRA search strategy
reactions	 Anaphylactic reaction (SMQ) – algorithmic
	Occurring during BMN 270 infusion or up to 48 hours post-
	infusion ^[a]
Thromboembolic events	MedDRA search strategy
	Embolic and thrombotic events (SMQ)

BIOMARIN	Study 270-203 Final Statistical Analysis Plan
----------	---

Name of EOSI	Definition	
AEs suggestive of thromboembolic	See Appendix for list of AE preferred terms	
events	In the time periods FVIII activity levels > 150%	
Development of anti-FVIII neutralizing antibodies	Reported as EOSIs with AE preferred term = "Anti factor VIII antibody positive"	
AEs suggestive of new diagnosis of malignancy (except non-melanoma skin cancer)	See Appendix for list of AE High Level Group Terms (HLGT) SOC = Neoplasm benign malignant and unspecified (including cysts and polyps)	

[[]a] If the number of hours post-infusion cannot be determined, AEs that start two days after the infusion day are excluded.

14.2 Clinical Laboratory Tests

Clinical laboratory tests include blood chemistry, hematology, urine tests, and coagulation will be presented in data listings, including the CTCAE v4.03 grade.

Liver tests by central labs will be assessed on a regular basis, as detailed in the protocol. ALT elevations including baseline ALT, time from infusion to ALT above ULN, time from infusion to ALT above 1.5xULN (and 3xULN, if applicable), peak ALT level, and total duration of ALT elevation, will be provided in a data listing.

In addition, incidences of potential drug-induced liver injury (DILI) that include an elevated ALT or AST in combination with either an elevated bilirubin or clinical jaundice, as defined by Hy's law, will be provided in a data listing.

14.3 Vital Signs and Physical Examination

Vital signs variables include systolic blood pressure, diastolic blood pressure, heart rate, respiration rate, and temperature. Vital signs will be provided in a data listing. Physical examinations will include assessments of general appearance; head, eyes, ears, nose, and throat; the cardiovascular, dermatologic, lymphatic, respiratory, gastrointestinal, genitourinary, musculoskeletal, and neurologic systems. Physical examination results (normal or abnormal) will be provided in a data listing.

14.4 Electrocardiogram and Liver Ultrasound

Electrocardiogram (ECG) and liver ultrasound are performed at the Screening visit with additional evaluations to be performed if clinically indicated during the study. Test results (normal, abnormal, unknown) will be provided in data listings.

14.5 Viral Shedding

Viral shedding will be extensively studied at Baseline, Day 2, Day 4, Day 8, Week 2, Week 3, Week 4, Week 6, Week 8, Week 12, Week 16, Week 20, Week 24, Week 26, every

4 weeks between Weeks 32-52, every 4 weeks (during Year 2), and every 6 weeks (during Years 3-5), until at least 3 consecutive negative results are obtained. Body fluids including blood, saliva, semen, urine and stool will be tested by polymerase chain reaction (PCR) at the time points. Testing of semen will continue at least through Week 12, even if 3 consecutive negative results have been recorded in that compartment prior to that time point. Subjects who have not had 3 consecutive negative semen samples by Week 26 should continue to have PCR testing in semen every 4 weeks until 3 consecutive negative samples are documented (or upon consultation between the Investigator and Medical Monitor).

Viral shedding will be provided in a data listing.

15 IMMUNOGENICITY ASSESSMENT

Assays to detect pre-existing immunogenicity specific for AAV5, including plasma derived inhibitors of transduction (transduction inhibition or TI) and total antibody (TAb) assays, will be tested at the Screening visit before BMN 270 infusion is given and at post-baseline visits according to the protocol's schedule of events. Test results (negative and positive with titer) will be provided in data listings.

Two assays are in place to determine immunogenicity to the human FVIII transgene product. The first is a total antibody (TAb) assay to detect binding antibodies in patient plasma directed against human FVIII and is reported as negative or positive with titer. The second is to evaluate neutralizing antibodies (NAb) capable of interfering with FVIII activity (FVIII Inhibitors) and is determined using the Bethesda assay with Nijmegen modification. This assay is reported out in Bethesda Units (BU), with a value of <0.6 considered negative. Both assays will be performed on patient plasma samples obtained at the screening visit, and at post-baseline visits according to the protocol's schedule of events. Test results will be provided in data listings.

Cellular immunity in the form of cytotoxic T lymphocytes (CTL) will be evaluated by Interferon-gamma (IFN-γ) ELISpot assay of peripheral blood mononuclear cells (PBMC). PBMC will be stimulated with overlapping peptide pools derived from the AAV5 capsid protein or human FVIII protein sequences to evaluate IFN- γ secretion by CTL targeting both the AAV5 capsid and the FVIII transgene product. Cellular immunity will be evaluated at baseline and at post-infusion visits according to the protocol's schedule of events and is reported as spot forming units (SFU) per 10^6 PBMC. A data listing will be generated reporting the number of SFU 10^6 PBMC for each peptide pool and control (positive and negative) stimulation for each patient at each study visit tested.

16 CLINICAL PHARMACOLOGY

Clinical pharmacology analyses will not be performed.

18 SUMMARY OF CHANGES TO STUDY SAP

v	ersion		
Number	Date	Affected Section(s)	Summary of Revisions
1.0	26MAR2024		Initial version

19 APPENDICES

19.1 Preferred terms suggestive of thromboembolic events

confusional state (10010305)	chest discomfort (10008469)
muscular weakness (10028372)	tachycardia (10043071)
swelling (100426740)	haemoptysis (10018964)
peripheral swelling-10030124)	presyncope (10026653)
odema Peripheral (10048959)	headache (10019211)
jaundice (10023126)	hypoaesthesia (10020937)
urine output decreased (10059895)	eye pain (10015958)
pain in extremity (10033425)	eye swelling (10015967)
erythema (10015150)	visual impairment (10047571)
dyspnea (10013968)	visual acuity reduced (10047531)

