19.0 APPENDICES

19.1 Preferred terms suggestive of thromboembolic events

confusional state (10010305)

muscular weakness (10028372)

swelling (100426740)

peripheral swelling-10030124)

odema Peripheral (10048959)

jaundice (10023126)

urine output decreased (10059895)

pain in extremity (10033425)

erythema (10015150)

dyspnea (10013968)

chest pain (10008479)

chest discomfort (10008469)

tachycardia (10043071)

haemoptysis (10018964)

presyncope (10026653)

headache (10019211)

hypoaesthesia (10020937)

eye pain (10015958)

eye swelling (10015967)

visual impairment (10047571)

[figure not shown]
visual acuity reduced (10047531)

SART Document Approval Form

Study name: 270-203

Study name: 270-200	
Overview	
Purpose (Check only 1): Final draft SAP Revision(s) to the final draft SAP Final SAP Amendment(s) to the final SAP The TOC of TLGs defined by the SAP	TLG mockups and specifications defined by a SAP Revision(s) to the TLG mockups and specifications document after its approval, determined by the Biostatistican to require SART approval Request(s) for major changes to mockups and specifications after review of TLG outputs produced for the Dry Run Other:
Comments	

CFT-116863- ITEM Rev. 00 Pg. 1 of 1

INTERIM ANALYSIS PLAN

Protocol Number:	270-203	
Study Title:	A Phase 1/2 Safety, Tolerability, and Efficacy Study of BMN 270, an Adeno-Associated Virus Vector–Mediated Gene Transfer of Human Factor VIII in Hemophilia A Patients with Residual FVIII Levels ≤ 1 IU/dL and Pre-existing Antibodies Against AAV5	
Sponsor:	BioMarin Pharmaceutical Inc. [name]	
Version:	2.0	
Date:	25 January 2021	

The information in this document is considered privileged and confidential by BioMarin Pharmaceutical Inc., and may not be disclosed to others except to the extent necessary to obtain Institutional Review Board approval and informed consent, or as required by Federal and State Laws. Persons to whom this information is disclosed must be informed that this information is privileged and confidential and that it should not be further disclosed.

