19 APPENDICES

19.1 Preferred terms Suggestive of Thromboembolic Events

Confusional State (10010305)

Muscular Weakness (10028372)

Swelling (100426740)

Peripheral Swelling-10030124)

Odema Peripheral (10048959)

Jaundice (10023126)

Urine Output Decreased (10059895)

Pain In Extremity (10033425)

Erythema (10015150)

Dyspnea (10013968)

Chest Pain (10008479)

Chest Discomfort (10008469)

Tachycardia (10043071)

Haemoptysis (10018964)

Presyncope (10026653)

Headache (10019211)

Hypoaesthesia (10020937)

Eye Pain (10015958)

Eye Swelling (10015967)

Visual Impairment (10047571)

Visual Acuity Reduced (10047531)

STATISTICAL ANALYSIS PLAN

Protocol Number: 270-203

Study Title: A Phase 1/2 Safety, Tolerability, and Efficacy Study of BMN 270, an Adeno-

Associated Virus Vector–Mediated Gene Transfer of Human Factor VIII in Hemophilia A Patients with Residual FVIII Levels \leq 1 IU/dL and Pre-existing

Antibodies Against AAV5

Sponsor: BioMarin Pharmaceutical Inc. [name]

Version: 1.0

Date: 26 March 2024

The information in this document is considered privileged and confidential by BioMarin Pharmaceutical Inc., and may not be disclosed to others except to the extent necessary to obtain Institutional Review Board approval and informed consent, or as required by Federal and State Laws. Persons to whom this information is disclosed must be informed that this information is privileged and confidential and that it should not be further disclosed.

Approvals

Statistical Analysis Plan

[figure not shown]
Title: A Phase 1/2 Safety, Tolerability, and Efficacy Study of BMN 270, an Adeno-

Associated Virus Vector-Mediated Gene Transfer of Human Factor VIII in Hemophilia A Patients with Residual FVIII Levels ≤ 1 IU/dL and Pre-existing

Antibodies Against AAV5

Protocol: 270-203, Amendment 4, 04 August 2021

Date: 26 March 2024

{See Appended Electronic Signature Pages}

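### As shown, Final SAP Appendix 19.1 omits chest pain, which both interim plans list, so one safety listing is defined more narrowly with no reason given

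*SAP*

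**What the plan says.** The SAP document holds three plans: Interim SAP v1.0 (11 March 2019), Interim plan v2.0 (25 January 2021) and Final SAP v1.0 (26 March 2024). In each, Table 1 of Section 14.1.5 has a row for adverse events suggestive of thromboembolism with two conditions. The first points to the appendix: "See Appendix for list of AE preferred terms". The second limits the row by FVIII activity: "In the time periods FVIII activity levels > 150" (in percent).

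Appendix 19.1 supplies the terms. Interim SAP v1.0 includes "chest pain (10008479" and Interim plan v2.0 includes "Chest Pain (10008479", in both cases between dyspnea and chest discomfort. The Final SAP sets the list in two columns. The left column ends at "dyspnea (10013968" and the right column begins at "chest discomfort (10008469". Chest pain appears in neither.

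The change log in Section 18 of the Final SAP records only an initial version, so it neither reports nor explains a removal.

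All three plans also print the code for swelling with nine digits: "swelling (100426740" in Interim SAP v1.0 and the Final SAP, and "Swelling (100426740" in Interim plan v2.0.

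**The concern.** The appendix is the only source of terms for this row, so a term that drops out of the appendix drops out of the definition. Applied as shown, the Final SAP would list a chest discomfort event in a qualifying period and leave out a chest pain event in the same period. Under either interim definition both would be listed.

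The omission looks accidental. It falls exactly at the column break, the other 20 terms keep their order and codes, and older slips in the list (an unbalanced parenthesis after peripheral swelling, the spelling of oedema, the swelling code) are carried over unchanged.

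At stake is traceability in a safety definition. The two interim analyses supported marketing applications, and the Final SAP describes itself as covering all study data. A definition that changes between them should change on the record.

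**Working it through.** **Inputs.** Appendix 19.1 of the three plans; Table 1 and Section 18 of the Final SAP; Sections 4 and 14.1.1 of the Final SAP for the context of the effect.

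**Step 1: count the terms.**

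| Plan | Layout | Terms | Chest pain |
|---|---|---|---|
| Interim SAP v1.0 | single list | 21 | item 11 |
| Interim plan v2.0 | single list | 21 | item 11 |
| Final SAP v1.0 | two columns, 10 + 10 | 20 | absent |

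**Step 2: compare item by item.** The left column of the Final SAP equals interim items 1 to 10, in order. The right column equals interim items 12 to 21, in order. The difference is 21 − 20 = 1 term, chest pain (10008479). No term was added.

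**Step 3: check the codes.** In the Final SAP 19 codes have eight digits and one, for swelling, has nine. In each interim plan 20 codes have eight digits and the same one has nine. The code error therefore does not distinguish the Final SAP from the interim plans.

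**Step 4: what each way of matching misses, relative to the 21 interim terms.**

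- By preferred-term name: chest pain only, 1/21 = 4.8%. Swelling is printed by name and is found.
- By printed code: chest pain and swelling, 2/21 = 9.5%.

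Table 1 refers to preferred terms, and the appendix heading does the same. No section says that events are matched on the numeric code. Matching by name is therefore the reading the text supports, and 1 of 21 is the relevant figure. It is a share of terms, not of events.

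**Step 5: can the row be populated?** It needs FVIII activity above 150%. Section 4 of the Final SAP states that enrolment ended after three subjects and that all three were below 5% after at least 6 weeks. The document gives neither their earlier values nor their levels after exogenous FVIII. The number of qualifying periods cannot be derived from it.

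**The case against.** The strongest objection is that the missing entry may not be missing from the sponsor's file. A list of 21 terms in two columns has 11 on the left and 10 on the right, so chest pain would stand alone in the last left cell, exactly where the gap is. The text at hand was read from a PDF, and such text can lose table cells. Interim plan v2.0, for example, shows the systemic hypersensitivity row of Table 1 without the SMQ line that the other two plans carry, and the Final SAP's table of contents has lost page numbers. Against this, the next two-column table, Appendix 19.2, kept just such a lone last left cell (Metastases). The text favours a real omission but does not prove one, so the source file must be checked first.

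The second objection is that no safety data are lost, and this stands. Section 14.1.1 lists every adverse event with its preferred term, Section 14.1.3 lists serious events separately, and diagnosed thromboembolic events have their own Table 1 row, through the Embolic and thrombotic events SMQ, with no FVIII restriction. With three subjects and no tabular summaries, a reader can find any chest pain record directly. What is affected is membership of one symptom-based listing.

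A reader might infer that swelling is missed too. The documents do not support that: the term is printed by name and Table 1 points to terms. Nor does the swelling code create a difference from the interim plans, since both carry it.

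**Conclusion.** The point holds for chest pain. As shown, the Final SAP defines this event of special interest with 20 terms where both interim plans use 21, and gives no reason. A chest pain event in a period with FVIII activity above 150% would be left out of the final listing although both interim definitions would have included it.

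The size is 1 of 21 terms and, in all likelihood, few or no records, given three subjects below 5% after at least 6 weeks. A reader might go further and infer that the final listing will disagree with the interim listings. That does not follow: nothing in the document shows that any subject had chest pain in a qualifying period. The definitions differ; whether the outputs do is unknown.

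The conclusion rests on two assumptions: that the appendix is complete as shown, and that matching is by preferred-term name. If the first fails, only the swelling code remains, as an editorial correction. If the second fails, swelling is lost as well, in the interim analyses as much as in the final one.

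**What to change.** 1. Check Appendix 19.1 in the source file of the Final SAP.
2. If chest pain is absent there, restore it with code 10008479, so that the list again has the 21 terms of both interim plans. If the removal was intended, document the reason in the SAP.
3. If the term is restored, re-run the listing for this row.
4. As a tidy-up, replace the nine-digit swelling code with the valid eight-digit MedDRA code, and confirm whether the program matched on name or on code. If on code, the re-run in step 3 must use the corrected code too.

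The cost is at most two entries in an appendix and one listing. No new data are needed, and the only visible effect would be any additional records that the corrected list brings in.
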